2.2 Primary Study Endpoints

- Reduced administration of antibiotics with a non-significant ($p>0.05$) effect on SSI rate

2.3 Secondary Study Endpoints

- Cost effectiveness (reduced total hospital costs)
- Timeliness of sample analysis
- Reduction in SSI

3 Subject Selection, Enrollment and Withdrawal

Any adult, male or female, over age 18, undergoing pancreaticoduodenectomy or total pancreatectomy for benign or malignant indication.

Target accrual: 140 patients.

3.1 Inclusion Criteria

- ≥ 18 yr M or F
- Undergoing pancreaticoduodenectomy or total pancreatectomy for any benign or malignant indication with informed consent

3.2 Exclusion Criteria

- Women who are pregnant
- Patients who are institutionalized or incarcerated
- Patients without the cognitive capacity to consent
- Patients undergoing emergency pancreaticoduodenectomy or total pancreatectomy
- Patients enrolled in similar clinical trials involving use of perioperative antibiotics

3.3 Subject Recruitment, Enrollment and Screening

Patients scheduled for pancreaticoduodenectomy or total pancreatectomy for benign or malignant indication at Mayo Clinic Rochester will be approached by the study team prior to their surgery if they meet the enrollment criteria. Recruitment methods may include electronic invitations to the study through the patient portal or email. After receipt of the initial study invitation, a study coordinator will contact the patient by phone to review the study and answer any questions. If the patient is interested in participating, the study coordinator will consent the patient via paper or electronic consenting methods.

3.3.1 When and How to Withdraw Subjects

Participants will be withdrawn from the study if they no longer meet enrollment requirements or wish to withdrawal consent. If a participant chooses to withdraw their consent, no additional testing or data collection will be performed.

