3.3.2 Data Collection and Follow-up for Withdrawn Subjects

Additional data collection during the follow-up period will not occur for subjects who have been withdrawn from the research study.

4 Study Device

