8.1 Confidentiality

Information about study subjects will be kept confidential and managed according to the requirements of the Health Insurance Portability and Accountability Act of 1996 (HIPAA). Those regulations require a signed subject authorization informing the subject of the following:

- What protected health information (PHI) will be collected from subjects in this study
- Who will have access to that information and why
- Who will use or disclose that information
- The rights of a research subject to revoke their authorization for use of their PHI.

In the event that a subject revokes authorization to collect or use PHI, the investigator, by regulation, retains the ability to use all information collected prior to the revocation of subject authorization. For subjects that have revoked authorization to collect or use PHI, attempts should be made to obtain permission to collect at least vital status (long term survival status that the subject is alive) at the end of their scheduled study period.

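### Withdrawal for lost eligibility is not confined to the time before randomisation, and it ends 90-day outcome collection for patients who have not withdrawn consent

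*Combined protocol and SAP*

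**What the plan says.** Section 3.3.1 gives two triggers. The first is loss of eligibility: "Participants will be withdrawn from the study if they no longer meet enrollment requirements". The second is a wish to withdraw consent. Its ban on further data is tied to the second only: "If a participant chooses to withdraw their consent, no additional testing or data collection will be performed". Section 3.3.2 is wider and gives no reason-specific exception: "Additional data collection during the follow-up period will not occur for subjects who have been withdrawn from the research study".

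The exclusion criteria in section 3.2 include "Patients without the cognitive capacity to consent" and "Patients who are institutionalized or incarcerated". The term institutionalised is not defined.

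Consent is obtained before surgery (section 3.3), and randomisation takes place during or after it (General Design). Section 5.3 takes the antibiotic, SSI and death outcomes from the medical record for 90 days after the operation. The trial is open (section 4.3). The primary endpoint requires less antibiotic use together with an SSI difference at p>0.05. SSI reduction is also a secondary endpoint, with success judged at p<0.1 under the Secondary Objective, and SSI appears among the stopping criteria in Table 7.

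For subjects who revoke authorisation, section 8.1 adds that "attempts should be made to obtain permission to collect at least vital status".

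**The concern.** Once a patient is randomised, eligibility normally plays no further part in whether outcomes are collected. Here it can. A patient who has agreed to data collection, and whose outcomes remain in the chart, can be withdrawn by the study and followed no further.

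If the reason for withdrawal is linked to a complicated recovery, the data that go missing are related to the outcome. The Background section itself links infectious complications to sepsis and acute respiratory failure, states in which capacity may be lost. Staff who apply the rule know the arm. The comparisons exposed are the SSI part of the primary endpoint, the antibiotic measures, the secondary SSI analysis and the Table 7 safety comparisons.

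**Working it through.** **1. Can the clause reach randomised patients?**
- Section 3.3.1 has no phrase tying loss of eligibility to the time before randomisation.
- Section 3.3.2 speaks of the follow-up period, so it governs data after surgery.
- Section 1.6 says direct participation ends once specimens are obtained. After that only chart abstraction remains, so what a later withdrawal removes is mainly outcome data.

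The text therefore permits it. It does not say that it will happen.

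**2. Does another section restore the data?**

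| Section | What it covers | Restores SSI or antibiotic data? |
|---|---|---|
| 6.2 | A modified ITT analysis; the modification is not defined | No |
| Handling of Missing Data | Lost samples and computer failure | No |
| 8.1 | Vital status, with permission, after revoked authorisation | No |
| 7.1, post-study events | Follow-up of unresolved adverse events; notice of deaths and events that may be study-related | Only in part |
| 7.2 | Follow-up of ongoing serious events to final outcome | Only in part |

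Mortality is better protected than SSI or antibiotic use.

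**3. What allowance does the plan make?** The stated sample size reproduces. With p1=0.54, p2=0.77, mean 0.655, two-sided alpha 0.05 and power 80%:

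n = [1.960·√(2·0.655·0.345) + 0.842·√(0.54·0.46 + 0.77·0.23)]² / 0.23² = 65.9, so 66 per group.

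The target of 70 leaves 4 per arm (4/70 = 5.7%), with no stated attrition rate. Power on this basis is 82.4% with 70 and 80.1% with 66, so precision is a minor matter. The issue is bias.

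**4. Size of a possible bias.** The number withdrawn and their SSI risk are assumptions. Take a true rate of 26.2%, which is the pilot's 9/42 at 30 days plus its two later cases (11/42), in an arm of 70. If w patients leave before an SSI is recorded and a share s of them have one:

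observed rate = (70·0.262 − w·s)/(70 − w)

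| w | s = 26.2% | s = 75% | s = 100% |
|---|---|---|---|
| 4 | 26.2% | 23.2% | 21.7% |
| 7 | 26.2% | 20.8% | 18.0% |

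With average risk (first column) there is no bias.

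**5. Worst-case effect on a test.** Assumed counts; unadjusted Pearson chi-square, Fisher's exact in brackets. The patients lost have SSIs not yet recorded at withdrawal.

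| Arm 1 | Arm 2 | Assumption | p |
|---|---|---|---|
| 17/70 | 10/70 | none lost | 0.134 (0.198) |
| 17/70 | 8/68 | two lost, Arm 2 only | 0.056 (0.077) |
| 17/70 | 7/67 | three lost, Arm 2 only | 0.033 (0.043) |
| 14/67 | 7/67 | three lost from each arm | 0.096 (0.153) |
| 18/70 | 30/70 | none lost | 0.033 (0.0496) |
| 18/70 | 28/68 | two lost, Arm 2 only | 0.054 (0.071) |

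The last two rows show the opposite risk: an SSI excess in Arm 2 moves to the passing side of the p>0.05 condition in the primary endpoint.

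**The case against.** The clause has an obvious innocent use. Consent precedes surgery and randomisation comes later, so eligibility can be lost in between, for example if the operation changes or becomes an emergency. That may be all the authors meant. It stands as a plausible reading, but the text is not limited to it, and one sentence would settle the matter.

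A reader might infer four stronger things, none of which the documents support:

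- **That patients who become delirious or ventilated, or go to a care facility, will be withdrawn.** Capacity is stated as capacity to consent, which a validly consented patient had. Institutionalised is undefined and stands beside incarcerated. No section says staff would apply either criterion after surgery.
- **That recorded SSIs are removed.** Section 3.3.2 stops additional collection only. SSI is assessed daily in hospital, and under section 8.1 data gathered before revocation stay usable. A patient who deteriorates because of an SSI would normally have it on record already. Later SSIs, antibiotic days and deaths are what could go missing.
- **That three patients would overturn the SSI result.** This needs every loss to fall in one arm and every lost patient to have an unrecorded SSI. With three lost from each arm, p is 0.096, not significant at 0.05. It falls just under the 0.1 used in the Secondary Objective by chi-square, but not by Fisher's test (0.153).
- **That 3.3.2 contradicts 8.1.** Section 8.1 seeks new permission for vital status, which is compatible with a default of no further collection. What is lacking is a cross-reference.

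The consent form is not in the reviewed copy, so what patients agreed to about data use after a study-initiated withdrawal cannot be seen.

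**Conclusion.** The concern holds as a defect in the rule, not as a demonstrated bias. As written, sections 3.3.1 and 3.3.2 allow outcome collection to end for a randomised patient who has not withdrawn consent, and no other section restores that patient's later SSI or antibiotic data. Whether this biases the comparison depends on three things the documents do not give: how many patients would be withdrawn, in which arm, and at what risk.

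The possible effect runs from zero, if withdrawn patients carry average risk, to the worst cases shown, where two or three unrecorded SSIs lost from one arm move p across a threshold. The effect on mortality is weaker. The rule should be changed because SSI is part of the primary endpoint, the arms are known, and the outcomes remain obtainable from the chart.

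**What to change.** - **Section 3.3.1:** state that withdrawal for lost eligibility applies only between consent and randomisation.
- **Section 3.3.2:** after randomisation, continue chart abstraction to day 90 for every patient unless consent or authorisation for data use is withdrawn. Keep all data collected before any withdrawal.
- **Section 6.2:** analyse all randomised patients in the arm assigned, and define the modified ITT set to match.
- **Section 3.3.2 again:** add a cross-reference to the vital-status request in section 8.1.

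No change to the sample size or to clinical care is needed. The cost is protocol and consent wording and a few more chart reviews by the same staff.

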3.3.2 Data Collection and Follow-up for Withdrawn Subjects

Additional data collection during the follow-up period will not occur for subjects who have been withdrawn from the research study.

4 Study Device

4.1 Description

Please refer to the manufacturing information/instructions for use provided by Oxford Nanopore Technologies for full device description. Briefly, the GridION MK1 is a ONT sequencing device that will be used to examine microbial DNA in bile cultures from subjects undergoing pancreatic head resection. The same GridION instrument (device ID GXB03025)

will be used to test each sample. Serial number/lot number information for the sterile, single time use flow cells/ reagents will be recorded on a device accountability log. MinKnow, Guppy, Porechop, BBMap, Centrifuge, and ResFinder 4.1 software will be used for data analysis. The GridION device will be stored in a secure laboratory and only be accessible to trained study staff. In the event the GridION needs replacement, we will contact the manufacturer for a replacement and validate performance using residual DNA from our published studies. A GridION instrument will be considered validated if microbial species are detected in the expected proportions. We will then record the new GridION serial number and date put into service for this study.

ONT sequencing and analysis will only be performed by our Postdoctoral Fellow trained in the technology, and there are no medical or surgical procedures involved in the use of the device

4.2 Method for Assigning Subjects to Treatment Groups

Two potential confounding variables exist in this patient population: operation type (pancreaticoduodenectomy vs total pancreatectomy) and pre-operative biliary stenting. Therefore, to eliminate potential bias between arms, patients will be stratified according to operation type (pancreaticoduodenectomy/total pancreatectomy) and biliary stenting (Y/N). Stratified patients will be assigned to arms by the study team using Medidata Rave with pre-determined assignments.

Given the prospective nature of this study, it will include subjects previously diagnosed with a specific disease and add newly diagnosed subjects in the future as patients are accrued.

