1.4 Clinical Data to Date

This study will use data that has been collected under the following research study: "Comparative Analysis of Bile Microorganisms in Patients Undergoing Major Hepatobiliary Operations", IRB# 19-011419 and published in two peer-reviewed journals^{44,48}. In brief, these studies involved analysis of intraoperative bile aspirate samples collected from 42 patients undergoing pancreatic head resection (total pancreatectomy, n = 9; pancreaticoduodenectomy, n = 33) at Mayo Clinic, Rochester (see Table 1 for patient characteristics). Metagenomic ONT sequencing was performed on bile aspirates to identify microbial species (bacterial, fungal) and antibiotic resistance genes. Sequencing results were then compared to bile cultures performed as part of Mayo Clinic's standard of care clinical practice to determine how ONT sequencing compared to current 'Gold Standard' culture practices^{44,48}.

To determine the optimum ONT protocol for detection of microbial species and antibiotic resistance genes present in the bile aspirates, different methods of DNA extraction, use of host DNA depletion, and use of different AMR gene databases were evaluated⁴⁸. In total, intraoperative biliary microbes were detected in 54.7% (23/42) of patients undergoing total pancreatectomy or pancreaticoduodenectomy using SC techniques. This included 35.7% (15/42) of patients with positive bacterial cultures, 2.4% (1/42) of patients with positive fungal cultures, and 16.7% of patients with positive fungal and bacterial cultures. The male sex, use of biliary instrumentation, and performance of vascular reconstruction during surgery was significantly correlated with the detection of biliary microbes.

Table 1: Clinical characteristics of patients included in our preliminary study

Clinical feature	Total	Biliary microbes ⁺	Biliary microbes ⁻	P value
Age, mean (IQR)	61 (22 - 71)	66.3 (46.3 - 81.3)	58.0 (18 - 82.6)	0.0858
BMI, mean (IQR)	26.4 (19 - 40.4)	26.3 (19 - 40.4)	26.4 (19.7 - 36.2)	0.9295
Sex, % male (n)	54.8 (23)	38.1 (16)	16.7 (7)	0.0375
Surgery indication, % (n)				0.892
Pancreatic ductal adenocarcinoma	45 (29)	50 (21)	19.0 (8)	
Intraductal Papillary Mucinous Neoplasm	7.1 (3)	0 (0)	7.1 (3)	
Neuroendocrine tumors	11.9 (5)	2.4 (1)	9.5 (4)	
Other	11.9 (5)	2.4 (1)	9.5 (4)	
ASM Score, mean (IQR)	2.6 (1 - 4)	2.7 (2 - 4)	2.5 (1 - 3)	0.1874
Type of surgery				0.9716
Total pancreatectomy, % (n)	21 (9)	11.9 (5)	9.5 (4)	

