Pancreaticoduodenectomy, % (n)	79 (33)	42.9 (18)	35.7 (15)	
Biliary instrumentation, % (n)	52 (22)	52.4 (22)	0 (0)	<0.0001
Vascular reconstruction, % (n)	38 (16)	31.0 (13)	7.1 (3)	0.0079

BMI, body mass index; IQR, interquartile range

Comparison of our optimized ONT sequencing protocol SC results revealed that our ONT protocol had identified 100% of biliary microbial contamination cases, detected 75% of cultured bacterial species and 76% of cultured fungal species, and predicted 81% of antibiotic resistance phenotypes observed using SC results ^{44,48}. With regards to detection of common biliary pathogens ^{3,54-57}, our ONT protocol improved detection of biliary candidiasis, detected 100% of cases of biliary *Escherichia coli* and biliary *Klebsiella*, and detected 83% of biliary *Enterobacter*, 76.5% of biliary *Enterococcus*, 93.8% of biliary *Streptococcus*. However, ONT did not detect one case of *Pseudomonas* infection and one case of *Staphylococcus aureus*, indicating as proposed in this study that SC techniques should be run alongside ONT protocols to ensure that no microbial species are missed. As for detection of pathogens of high clinical concern (i.e. ESBL, CRE species), ONT similar detection rates compared to SC, and potentially improved detection of *E. coli*, *K. oxytoca*, *K. pneumoniae*, and *Citrobacter freundii*. Overall, ONT improved detection of microbial species (particularly with regards to anaerobic species and fungal species) and predicted a significantly higher number of antibiotic resistance phenotypes than were identified using SC. Significantly, the results turnaround for ONT sequencing was just 14 hours compared to an average turnaround time of 98 hours for SC. On average, it took 4.8 days (range = 1 – 15 days) to complete microbial identification and an additional 2 days (range = 0 – 9 days) to complete AST for the culture positive samples. Delays greater than 5 days in completing microbial identification occurred in samples with multiple aerobic species of the same genus (*Enterococcus* spp., *Klebsiella* spp., *Streptococcus* spp.), anaerobic species (*Schaalia (Actinomyces) turicensis*, *Finegoldia magna*, *Veillonella* sp., *Actinomyces johnsonii*, *Parvimonas micra*), and/ or fungal species *Saccharomyces cerevisiae*, *Candida* spp.), and on average, optimal antimicrobial therapy was delayed for 7 days. Use of a test that would enable microbial identification and prediction of AMR phenotypes within 24hrs post-surgery, would, therefore, have significantly shortened the delay in patients receiving optimized tailored antimicrobial therapy post-surgery.

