2.1 General Design

This will be a prospective 1:1 randomized controlled trial with the following study arms:

Arm 1: Patient Group 1

Standard Care Only. Patients will undergo intra-operative bile aspiration (as is routinely performed) with SC of the aspirate. All patients will receive standard prophylactic antibiotics according to practice standards and will be continued for up to 5 days as is routine. If bile cultures are positive, antimicrobials will be continued for a complete 10-day course of antibiotics (Figure 2).

Arm 2: Patient Group 2

Standard Care + ONT. Patients will undergo intra-operative bile aspiration (as is routinely performed) with standard cultures AND ONT sequencing of the aspirate. All patients will receive standard prophylactic antibiotics according to practice standards. ONT sequencing results will be made available to providers through electronic medical record (EMR) and team electronic notifications. Patients with negative ONT results will be taken off the standard prophylactic antibiotics and patients with positive ONT results will have antimicrobial therapy adjusted according to ONT sequencing results. However, if SCs are positive or suggest alternative/broader coverage then these results

will guide therapy and not ONT results. If bile cultures are positive, antimicrobials will be continued for a complete 10-day course of antibiotics (Figure 2).

[figure not shown]

Figure 2: A schematic diagram of our proposed study to investigate the use of Oxford nanopore sequencing to detect and characterize biliary microbial contamination

The study will include patients undergoing elective pancreaticoduodenectomy or total pancreatectomy for any clinical indication. Patients will be excluded from the study if they are < 18 years of age, enrolled in any similar clinical trials involving use of peri-operative antibiotics, are undergoing distal pancreatectomy, or undergoing emergency total pancreatectomy or emergency pancreaticoduodenectomy (Table 4). Following recruitment to the study, patients will be randomly assigned intraoperatively/post-operative to either the control group (Arm 1) or the interventional group (Arm 2). We will use stratified randomization with age (below 65 years vs 65 years and above), sex, operation type (pancreaticoduodenectomy vs total pancreatectomy), biliary stenting (yes vs no), and patient ASA score as stratification factors.

Table 4: Patient inclusion and exclusion criteria for the clinical trial

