Inclusion Criteria	
 • > 18 years of age • Scheduled for elective total pancreatectomy or pancreaticoduodenectomy
Exclusion Criteria	
 • < 18 years of age

	
• Emergency total pancreatectomy or pancreaticoduodenectomy• Patients scheduled for distal pancreatectomy• Women who are pregnant• Patients without the cognitive capacity to consent• Patients enrolled in similar clinical trials involving use of perioperative antibiotics
--	--

Bile will be collected via bile duct aspiration. Bile aspiration will be performed with a 16-gauge needle and 3 cc syringe prior to bile duct division (Figure 3), and aspirated material will be aseptically transferred into sterile aerobic and anaerobic transport vials. Samples will be concurrently transported to the Pathology lab and the microbiome lab to undergo SC techniques and ONT sequencing, respectively. Standardization of bile collection and surgical procedure will be assured as all surgeries will be performed by the same lead surgeon, [name]. Surgical variables that have been associated with increased SSI risk will be recorded. This will include patient sex, age, BMI, ASA score, the volume of blood loss, whether the patient had a biliary stent inserted prior to surgery, closure technique, and whether vascular reconstruction was performed during surgery.

[figure not shown]

Figure 3: Collection of intraoperative bile aspirate during pancreatic head resection (total pancreatectomy, pancreaticoduodenectomy)

SCs obtained from intraoperative bile aspiration for both study arms will be performed in compliance with clinical standards. This is routinely performed by the Pathology lab and no changes to these protocols are necessary (see Supplementary Materials S1 – S6) for culture methods and AST protocols). Results will be reported in the EMR which will be accessible by the clinical team, as is the current clinical practice. ONT sequencing for those assigned to Study Arm 2 will be performed on a 1cc liquid bile sample collected fresh from the operating room after specimen release from the Pathology lab. Approval from our institutional TRAG

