5.1 Enrollment Visit

At the time of enrollment, the informed consent will be reviewed with the participant and informed consent will be obtained.

Consented patients will be de-identified in compliance with the Health Insurance Portability and Accountability Act of 1996 (HIPAA) and patient identifiers will be stored electronically with access limited to members of the research team on a need-to-know basis. Patient demographics and baseline collection information will be gathered from the participant's medical record and documented in the Medidata Rave database. Demographics and baseline collection data collection will include age, sex, indication for surgery, ASA, major comorbidities, pre-operative biliary stenting/manipulation, and pre-surgical cholangitis, etc.

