5.2 Sample Collection Visit

Following enrollment procedures, 2 cc of residual bile collected during surgery will be aliquoted into cryovial and placed on ice (not frozen). It will be picked up by the study team at the time of collection for ONT sequencing. Tissue Request Acquisition Group (TRAG) approval will be requested for managing of samples. The sample will be aliquoted from the clinical collection and so collection will not add additional time to the surgery procedure. Participants will be randomized in Medidata Rave to a study arm based on operation type and pre-operative biliary stenting using a dynamic stratification. Participants will be randomized in a 1:1 ratio.

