- Diabetes mellitus co-morbidity at time of surgery (clarifications needed for data collection)
- Cancer diagnosis
- ASA score at time of surgery
- Administration of chemotherapy prior to surgery (from what timepoint or date of last chemo?)
- Presence of biliary stent at time of surgery
- Blood loss during surgery
- Length of surgery (skin to skin, open to close?)
- Vascular reconstruction (arterial, venous) during surgery
- Closure technique
- Pancreatic leak risk score (when done? In record?)
- Surgical drains (what is needed)
- Post-op TPN

Variables with p-values less than 0.15 will be considered as potential candidates for a multivariable model. We will report odds ratios and 95% confidence interval. The area under the receiver operating characteristic (ROC) curve will be estimated as a measure of the ability of the model to discriminate between patients who had SSI within 90 days versus those who did not. An area under the ROC estimate of 0.7–0.8 will be regarded as acceptable, 0.8–0.9 will be regarded as excellent, and more than 0.9 will be regarded as outstanding.

We will also assess cost effectiveness of using ONT compared to SC. To achieve this, we will compare the cost to perform SC testing and ONT testing against costs associated with post-operative patient care. This will include the total cost to administer perioperative antibiotics, costs associated with length of hospital stay, and the costs associated with the need of additional procedures and tests associated with SSI (i.e. post-operative SC and antibiotic susceptibility testing, additional antibiotics, wound debridement, abdominal abscess drainage, CT scan, US scan).

For continuous variables, t-test will be performed and for binary variables chi-square or fisher's exact testing will be performed as appropriate. Additional analysis will be performed as necessary to determine differences in study arms. Should additional analysis beyond the scope of our abilities is necessary then a statistician will be employed.

Inpatient related costs associated with each intervention arm will be analyzed and compared with the assistance of the Robert D. and Patricia E. Kern Center for Science of Health Care in order to understand the economic impact of each intervention arm.

Handling of Missing Data

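### The trial stratifies on undefined pre-operative biliary stenting, but the candidate covariate is a stent present at surgery; the baseline item closest to the pilot's predictor is used for neither

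*Combined protocol and SAP*

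**What the plan says.** **Randomisation.** Section 2.1 General Design lists "biliary stenting (yes vs no), and patient ASA score as stratification factors", after age, sex and operation type. Section 4.2 says "patients will be stratified according to operation type (pancreaticoduodenectomy/total pancreatectomy) and biliary stenting (Y/N". Section 5.2 says that randomisation is "based on operation type and pre-operative biliary stenting using a dynamic stratification". All three name stenting. None says which devices count, over what period, or what happens when a stent has been removed.

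**Data collected.** Section 2.1 records "whether the patient had a biliary stent inserted prior to surgery" as a surgical variable. Section 5.1 collects "pre-operative biliary stenting/manipulation, and pre-surgical cholangitis" at baseline.

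**Analysis.** The covariate list in 6.2 has "Presence of biliary stent at time of surgery". The listed variables are assessed for inclusion, and those with p below 0.15 become candidates for the multivariable model. Section 6.2 also ties regression adjustment to baseline imbalances. The primary success criterion (2.2 Primary Objective) asks for a result corrected for key covariates.

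**Pilot.** Section 1.4 reports: "The male sex, use of biliary instrumentation, and performance of vascular reconstruction during surgery was significantly correlated with the detection of biliary microbes". In Table 1, all 22 patients with biliary instrumentation had biliary microbes.

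**The concern.** The wordings are not interchangeable. A patient whose stent was taken out before the operation is a yes for a stent inserted before surgery and a no for a stent present at surgery. A patient drained or manipulated without a stent is a yes on the baseline item and a no on the covariate. Section 1.1 describes stenting as the commonest form of drainage, so it is not the only form.

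The factor matters because bile status sets planned antibiotic duration, and duration is a primary outcome. Under 2.1, Arm 1 patients receive up to 5 days, or a 10-day course if cultures are positive. Under 2.1 and Table 5, antibiotics stop early in Arm 2 when sequencing is negative. A baseline variable that nearly determines bile status would therefore explain much of the predictable variation in duration. The plan collects such a variable but does not use it, and it may adjust for a narrower one that differs from the stratum.

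**Working it through.** **1. The plan's own figure.** Section 6.1 gives 66 per group for 54% against 77% positivity, 80% power and alpha 0.05. The two-sided pooled-variance formula without continuity correction returns 66; power at 70 per arm is 0.82. The stenting factor does not enter this formula, so nothing here changes N.

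**2. Pilot table.** Table 1 gives 22 instrumented patients, all microbe-positive. Section 1.4 gives 23 of 42 positive by culture. By subtraction, 1 of 20 non-instrumented patients was positive and 19 were negative. With no negatives among the instrumented, phi² = a·d / [(c+d)(a+c)], where a = positives coded yes, c = positives coded no and d = negatives coded no. So phi² = 22×19 / (20×23) = 0.909.

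**3. Share coded differently.** Let q be the share of instrumented patients without a stent at surgery. The documents do not give q, so it is assumed. At q = 20%, 4.4 of the 22 move to the no row: phi² = 17.6×19 / (24.4×23) = 0.596. Scaled to 140 patients, 4.4×140/42, or about 15, change group.

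**4. Precision.** Assumed durations are 5 or 10 days in Arm 1 and 1 or 10 days in Arm 2, fully determined by the result. With 70 per arm, SE = √{[25·v₁(1−R₁²) + 81·v₂(1−R₂²)]/70}, where v = p(1−p) and R² is the phi² for the result that drives each arm. The formula lets the factor's effect differ by arm and takes the observed mix of the factor as given.

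- *Arm 2 follows culture:* p = 23/42 and v = 0.2477 in both arms.
- *Arm 2 follows sequencing at the 77% of section 6.1:* take 32 of 42 positive, v₂ = 0.1814. All 22 instrumented patients are sequencing-positive, since 1.4 says sequencing found every contaminated case. That leaves 10 of 20 positive among the rest, so phi² = 22×10 / (20×32) = 0.344. At q = 20% it is 17.6×10 / (24.4×32) = 0.225. Ten days is assumed for every sequencing-positive patient.

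| SE in days | Arm 2 follows culture | Arm 2 follows sequencing |
|---|---|---|
| Unadjusted | 0.61 | 0.55 |
| Adjusted for instrumentation (also q = 0) | 0.19 | 0.38 |
| Adjusted for stent at surgery, q = 10% | 0.31 | 0.42 |
| q = 20% | 0.39 | 0.45 |
| q = 30% | 0.44 | 0.47 |

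Both columns are needed because the documents conflict. Section 1.1 says sequencing agreed perfectly with negative cultures, which does not fit 77% against 54%. The Arm 2 text in 2.1 and the last row of Table 5 also differ on which result governs treatment; those passages must be reconciled.

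**5. Balance.** Suppose the stratifier itself codes k of the 22 instrumented pilot patients as no. Scale to 140 patients and assume exact 1:1 balance within strata. The yes stratum is all positive and contributes nothing. The no stratum, of size n with proportion p positive, gives a count variance per arm of (n/2)²·p(1−p)/(n−1). The SD of the arm difference in bile positivity is twice the square root of this, divided by 70: 2.6 percentage points at k = 0, 5.2 at k = 4, and 8.4 with no stratification. This k need not equal q: on a natural reading, a removed stent still counts as pre-operative stenting.

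**The case against.** Several points against this stand.

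- A reader might infer that the stratifier is defined four ways. It is not. Sections 2.1, 4.2 and 5.2 all call it biliary stenting, and a stent inserted before surgery is plausibly the same thing. The real variants are the broader baseline item and the narrower covariate.
- A reader might infer that nothing in the plan matches the pilot's variable. The baseline item comes close, although the pilot never defines instrumentation. All 22 pilot patients may have had a stent in place, in which case q = 0 and nothing is lost.
- A reader might infer that a stent at surgery is fixed in the model. It is only a candidate. The adjusted SEs therefore describe a model that the plan permits but does not commit to. Equally, nothing guarantees that the stratum enters the analysis.
- Stenting is a defensible factor: section 1.1 cites numerous studies linking it to surgical site infection. This supports keeping the stratum, and the fix does so. It does not supply a definition or make the covariate agree with the stratum.
- The contrast of 0.19 with 0.39 days holds only if Arm 2 follows culture. Under the plan's own 77% it narrows to 0.38 against 0.45.

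**Conclusion.** The point holds as a mismatch between the randomised stratum, the candidate covariate and the best available baseline predictor. The cost is balance and precision only. The documents do not support a claim that the mismatch biases the comparison of arms: allocation remains random whichever way a patient is coded, and N and the type I error are unaffected.

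Nor do they show that patients would land in a stratum at low risk of infection. Any lower risk is of bile contamination. Only 4 of 9 pilot patients with infection within 30 days had positive bile, against 19 of 33 others by subtraction (Fisher p = 0.71, assuming those 4 are among the 23 culture-positive patients).

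The size is illustrative. It rests on a 42-patient pilot, an assumed q, and durations that follow the test result exactly. Off-protocol variation would make real differences smaller. At q = 20% the SE is about twice as large in one scenario (0.39 against 0.19 days) and about a sixth larger in the other (0.45 against 0.38).

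**What to change.** In 6.2, replace the stent-at-surgery covariate with two prespecified terms in the primary adjusted model, both kept without p-value screening:

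- (a) the stenting stratum as used at randomisation;
- (b) any pre-operative biliary instrumentation, taken from the 5.1 item.

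If the two coincide in the data, one term is enough. Write one definition covering device types, drainage without a stent, other duct manipulation, stents removed before surgery, and the time window. Use it in 2.1, 4.2, 5.1, 5.2 and 6.2. If randomisation has already begun on stenting yes or no, the stratum stays as it is and (b) is simply added.

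This is a free improvement. The data are already collected at enrolment; the only cost is wording and possibly splitting one case report form field into stent and other manipulation. Sample size and alpha are unaffected.
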